## 8.5. Subject Withdrawal Criteria

An early termination occurs when a subject who provides written informed consent ceases participation in the study, regardless of circumstances, before the completion of the study. Subjects may be voluntarily discontinued from study medication or withdrawn from the study at any time for any reason. In addition, the Principal Investigator or Medical Monitor may discontinue the study drug administration or terminate a subject's study participation due to any of the following reasons:

- AE (e.g., not compatible with study continuation)
- Non-compliance with study drug
- Lack of efficacy (e.g., IOP exceeds 34 mmHg in either eye after randomization)
- Progressive disease
- Protocol deviation (e.g., not fulfilling eligibility criteria)
- Pregnancy
- Voluntary withdrawal by subject at any time for any reason
- Lost to follow-up (e.g., no contact is possible)
- Death
- Other

If the study drug administration is discontinued prior to Visit 5, they should be encouraged to still participate in all follow-up study visits until Visit 5 on an observational basis.

[figure not shown]
If the study drug administration is discontinued prior to Visit 5, then to the extent possible, all procedures for Early Termination will be performed on the day of early drug discontinuation as per [Table 3](#) (for adult subjects) or [Table 4](#) (for pediatric subjects). Subjects who are discontinued from the study early will not be replaced.

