3.3. Sample Size Planning

The sample size calculation was based on a two-sided Type I error rate of 5% and a non-inferiority margin of 1.5 mmHg. Assuming a treatment difference of 0 mmHg between the DE-117 arm and the Timolol arm, a standard deviation (SD) of 4.0 mmHg, and a correlation coefficient of 0.6 among repeated measures, approximately 400 adult subjects in total (200 subjects per treatment arm) will provide 90% power to demonstrate non-inferiority of DE-117 Ophthalmic Solution 0.002% to Timolol Maleate Ophthalmic Solution 0.5% in IOP-lowering effect.

The standard deviation of 4.0 mmHg was determined from previous DE-117 studies conducted in the United States: 33-002 and 33-003.

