6.2. Handling of Missing Data

6.2.1. Efficacy Measures

For subjects with the use of any non-study IOP-lowering therapy to lower IOP, unless otherwise specified, the IOP data collected after the non-study IOP-lowering therapy will be censored (treated as missing) in efficacy analyses.

For each IOP endpoint, no imputation is needed for the analysis on observed cases using the mixed-effects model for repeated measures (MMRM). Sensitivity analysis will be performed using a Pattern-Mixture Model (PMM) approach.

In the PMM approach, Multiple Imputation (MI) with mixed missing data mechanisms will be used to investigate the appropriateness of the missing at random (MAR) assumption for missing values resulting from censoring due to the use of IOP-lowering rescue therapy, or resulting from study discontinuation due to lack of efficacy or AE.

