7. SUMMARY OF STUDY POPULATION DATA

7.1. Subject Disposition

The disposition of ITT population (i.e., all randomized subjects) will be summarized by treatment and overall. The summary will include the number and percentage of ITT subjects in the Safety population, FAS, and PPS. The disposition summary will also include the number and percentage of subjects who completed the study drug, subjects who discontinued the study drug prematurely but continued with study participation and among which who completed or not completed all study visits, as well as the number and percentage of subjects who discontinued from the study or discontinued from the study drug prior to Month 3 Visit by the primary discontinuation reason.

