8.1.2. Sensitivity Analyses

For the primary endpoint and the key secondary endpoints, sensitivity analyses will be performed to assess the robustness of the results from the primary analysis. The sensitivity analyses consist of two types: (1) assessment based on the PPS and (2) a pattern-mixture model (PMM) approach ([Table 6](#)). Unless otherwise specified, for subjects who receive IOP-lowering rescue therapy, any IOP values collected after the receipt of rescue therapy will be censored (i.e., treated as missing) in the analyses.

Table 6: Overview of Primary and Sensitivity Analysis Methods

Primary or Sensitivity Analysis	Statistical Method	Analysis Population	Handling of Missing Data
Primary Analysis	MMRM	FAS	Observed cases
Sensitivity Analyses	MMRM	PPS	Observed cases
	PMM with delta-adjustment	FAS	MI

Abbreviations: FAS = full analysis set; MI = multiple imputation; MMRM = mixed-effects model for repeated measures; PMM = pattern-mixture model; PPS = per protocol set.

To assess the sensitivity to departure from MAR assumption, a PMM with delta-adjustment will be applied, as follows:

- a. Use Markov chain Monte Carlo (MCMC) to create monotone missingness first. Then obtain standard multiple imputations under MAR assumptions for missing IOP values using monotone regression. The missing data are filled in and 50 complete datasets are created. The seed that will be used in the SAS program is 13546.
- b. For each IOP value that had been missing because of (1) censoring after having received IOP-lowering rescue therapy; or because of (2) early study discontinuation due to lack of efficacy or AE, regardless of treatment arm, adjust these values by adding delta to the imputed values, where delta = 1.0 mmHg. The seed that will be used in the SAS program is 13546.
- c. Each of the 50 complete datasets will then be analyzed separately using the same MMRM as used for the primary analysis.
- d. The estimates obtained from the MMRM analysis of each complete dataset are combined for inference purposes.
- e. Repeat step b, c, d, with delta = 2.0, 3.0, 4.0, and 5.0 mmHg. The larger the value of delta that is required to reverse the conclusion of the primary analysis, the more robust the conclusion is considered to be.

The main part of the SAS code for the specified MMRM analysis and PMM are provided in Appendix A ([Section 12.1](#)) and Appendix B ([Section 12.2](#)), respectively.

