For the primary endpoint, in addition to the two types of sensitivity analyses described above, if the overall rate of study drug discontinuation due to lack of efficacy or AE is greater than 10% and the difference between the rate in the DE-117 and Timolol arms is greater than 5 percentage points, a trimmed mean analysis ([Permutt et al., 2017](#)) will be conducted as a sensitivity analysis.

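### The delta-adjusted sensitivity analysis adds no delta for unrescued subjects who stop study drug for lack of efficacy or AE and whose later IOP is missing for another recorded reason

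*SAP*

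**What the plan says.** SAP 8.1.2 step a imputes all missing IOP values under missing at random (MAR) and produces 50 completed datasets. Step b then adds delta, first 1.0 mmHg and in repeats 2.0 to 5.0 mmHg, to two groups only: values missing because they were censored after rescue therapy, and values missing because of "early study discontinuation due to lack of efficacy or AE, regardless of treatment arm". SAP 6.2.1 describes the second group in the same terms, as missing values "resulting from study discontinuation due to lack of efficacy or AE". The wording therefore agrees across the two sections and is not a slip in one of them.

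Elsewhere the documents keep stopping the drug apart from leaving the study. Protocol 7.4.6, Protocol 8.5 and SAP 3.4 encourage subjects who stop drug to keep attending up to Visit 5. Protocol 8.5 defines early termination by the end of study participation. The disposition summary in SAP 7.1 counts "subjects who discontinued the study drug prematurely but continued with study participation and among which who completed or not completed all study visits". The trimmed-mean analysis at the end of SAP 8.1.2 is triggered by the drug event: it runs "if the overall rate of study drug discontinuation due to lack of efficacy or AE is greater than 10"% and the rates in the two arms differ by more than 5 percentage points.

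**The concern.** The delta is meant to test whether the conclusion survives if failures have worse IOP than MAR predicts. Step b recognises failure only through rescue or through the recorded reason for leaving the study. The plan itself foresees people who stop drug, stay on, and do not complete every visit. If such a person stopped because of lack of efficacy or AE and took no rescue, a later missed visit, or a later exit recorded as voluntary withdrawal or loss to follow-up, brings no delta. Nothing in the available text carries the reason for stopping drug forward to later missing values.

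This matters because little else tests MAR. SAP 10.3 drops the protocol's LOCF analysis on the ground that the pattern-mixture model is enough. The per-protocol analysis is again an observed-case MMRM, and the trimmed mean is conditional. The pattern-mixture model is thus the only unconditional check, and step e reads robustness from the size of delta needed to overturn the result. Subjects who are off drug because treatment failed, and then missing, are among those for whom MAR is least credible.

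**Working it through.** **Who is left out.** Take a subject who has stopped drug for lack of efficacy or AE.

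| What happens next | Treatment of later IOP |
|---|---|
| Receives rescue; later values censored | Delta, first condition |
| Leaves the study; exit reason lack of efficacy or AE | Delta, second condition |
| No rescue; attends visits | Observed; nothing to impute |
| No rescue; stays, then misses a visit or leaves for another recorded reason | MAR, no delta |

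Only the last row is uncovered.

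**Inputs and the plan's own figure.** SAP 3.3 gives a "two-sided Type I error rate of 5% and a non-inferiority margin of 1.5 mmHg". It takes the true difference between the arms as zero, and its variability inputs are "a standard deviation (SD) of 4.0 mmHg, and a correlation coefficient of 0.6 among repeated measures". With 200 per arm it states 90% power. For one timepoint, 150 per arm gives 90% power and 200 per arm gives 96.3%. For the nine-timepoint rule (400,000 simulated trials, exchangeable correlation):

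- SD 4.0, correlation 0.6: 83.9% for all nine limits at or below 1.5, and 72.5% once the five-of-nine criterion at 1.0 is added.
- SD 3.2 after baseline adjustment: 98.0% and 92.0% (residual correlation 0.6), or 97.5% and 94.1% (residual correlation 0.375).

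The stated 90% is approached only on the baseline-adjusted reading. The SAP does not show its formula, and the present point does not depend on it.

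**Precision at one timepoint.**

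- Unadjusted: SE = 4.0 × √(2/200) = 0.40; half-width 1.96 × 0.40 = 0.784 mmHg.
- Baseline-adjusted, assuming that the 0.6 also applies between baseline and follow-up: SD = 4.0 × √(1 − 0.36) = 3.2; SE = 3.2 × √(2/200) = 0.32; half-width 0.627 mmHg.

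**Omitted shift.** After imputation the data are near complete, so the omitted shift at an affected timepoint is approximately

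shift = delta × (p for DE-117 − p for timolol),

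where p is the share of the arm in the last row of the first table. The documents give no p, so the gap is assumed:

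| Gap (percentage points) | delta = 1 | delta = 5 |
|---|---|---|
| 0 | 0 | 0 |
| 1 | 0.01 | 0.05 |
| 2.5 | 0.025 | 0.125 |
| 5 | 0.05 | 0.25 |

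A 5-point gap equals the between-arm threshold for the trimmed mean, with every extra drug-stopper uncovered. It is a high value for a subset.

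**Against the decision rule** (SAP 8.1.1.1: all nine upper limits ≤ 1.5 and at least five ≤ 1.0). Take an observed difference of 0, hold the SE fixed, and use the largest shift, 0.25.

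- SE 0.40: affected limits move from 0.784 to 0.784 + 0.25 = 1.034.
- SE 0.32: affected limits move from 0.627 to 0.627 + 0.25 = 0.877.

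If the missing visit is Month 3, three of the nine limits are affected. At SE 0.40 the other six stay at 0.784, so six of nine meet 1.0, all nine meet 1.5, and non-inferiority stands. To fail the five-of-nine criterion, at least five limits would have to exceed 1.0. The maximum shift would then have to act at a second visit too, at the unadjusted SE. At SE 0.32 no limit reaches 1.0.

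**The case against.** Several points on the other side stand.

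- A reader might infer that every drug-stopper who later misses visits escapes the delta. The documents do not support that. Rescue brings delta whatever the drug status, and so does a study exit coded to lack of efficacy or AE. Protocol 8.5 has one list of reasons for both kinds of discontinuation, and how often the two recorded reasons would differ is unknown.
- A reader might infer that SAP 8.1.2 contradicts itself by using the study event in step b and the drug event for the trimmed mean. It does not. The trimmed-mean condition triggers a different method and does not define which values receive delta. The point is incomplete coverage.
- Uncovered subjects are not simply given on-drug values of other people. Protocol 7.4.6 and 8.5 ask for the exit procedures, including IOP, on the day drug is stopped, as far as possible. Under SAP 4.1.5 an IOP from Day 62 onward maps to Month 3 and one from Days 23 to 61 maps to Week 6. Some subjects therefore have an observed value, and for others the exit reading feeds the imputation. That narrows the gap but does not close it: a reading on the day of stopping says little about IOP weeks later, off drug.
- The SAS code for the model is assigned to Appendix B, which is not in the text available here. Its flag may already be wider. If so, the prose still needs to match it.

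**Conclusion.** The gap is real but narrow. As written, unrescued subjects who stop drug for lack of efficacy or AE, stay for observation, and then have IOP missing for another recorded reason get no delta at any value from 1 to 5 mmHg. With assumed between-arm gaps of 1 to 5 points, the omitted shift is 0.01 to 0.25 mmHg, against a confidence-interval half-width of 0.63 to 0.78 mmHg. It is about zero if the arms are equal. The omission flatters DE-117 only if DE-117 has more such subjects; if timolol has more, it is conservative.

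The size rests on gaps that the documents do not supply, on near-complete data after imputation, and on an unchanged SE. The primary MMRM is not affected. A reader might infer that the omission hides a reversal of non-inferiority, but the calculation does not show one: even the largest shift considered, applied to Month 3, leaves six of nine limits within 1.0. A reader might also want "Progressive disease", a separate reason in Protocol 8.5, to attract the delta. That is a judgement call and is not part of this point.

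**What to change.** In SAP 6.2.1 and in 8.1.2 step b(2), replace the study-discontinuation condition with: any missing IOP after discontinuation of study drug or study due to lack of efficacy or AE. Make the flag in the Appendix B code match, and settle both before unmasking so that the choice cannot be read as data-driven.

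The cost is one revised condition, carried into both sections, and one program flag. SAP 7.1 already tabulates the reasons for discontinuing drug and study, so no new data are needed. The downside is that the tipping-point result may look slightly less favourable.

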Non-inferiority criteria for primary endpoint: With respect to the primary study objective, non-inferiority of DE-117 to Timolol is achieved if the upper limit of the two-sided 95% confidence interval for the difference in the mean IOP (DE-117 minus Timolol) is ≤ 1.5 mmHg at all nine timepoints and ≤ 1.0 mmHg at a majority (five or more) of the nine timepoints.

Superiority of DE-117 to Timolol for the primary efficacy endpoint is achieved if the upper limit of the two-sided 95% confidence interval for the difference in the mean IOP (DE-117 minus Timolol) is < 0 mmHg at all nine timepoints.

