10.3. Sensitivity Analysis of the Primary and Secondary Efficacy Endpoints

Protocol Amendment 1 (Version 1.1) Section 14.5, Handling of Missing Values, specified a sensitivity analysis of the primary efficacy endpoints and the secondary binary IOP endpoints (Month 3) in which missing values would be imputed using the last-observation-carried-forward (LOCF) approach. The LOCF approach is removed from the sensitivity analyses because the PMM generalizes the MMRM to include mixed missing data mechanisms beyond the MAR assumption of the MMRM. Thus, the PMM is sufficient to evaluate the robustness of the results from the MMRM.

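### The delta-adjusted sensitivity analysis adds the same penalty in both arms, so with similar flagged missingness it hardly tests non-inferiority; a DE-117-only or two-way delta grid should be added

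*SAP*

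**What the plan says.** SAP section 6.2.1 gives the purpose of the pattern-mixture analysis: it "will be used to investigate the appropriateness of the missing at random (MAR) assumption" for values lost to rescue censoring or to study discontinuation for lack of efficacy or AE. Section 8.1.2 imputes under MAR (50 datasets). For the flagged values it then says to "regardless of treatment arm, adjust these values by adding delta to the imputed values, where delta = 1.0 mmHg". Step e repeats this at 2, 3, 4 and 5 mmHg and reads the result as follows: "The larger the value of delta that is required to reverse the conclusion of the primary analysis, the more robust" the conclusion is taken to be. No arm-specific delta appears.

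The other sensitivity analyses are an observed-case MMRM on the PPS and, for the primary endpoint only, a trimmed mean. The trimmed mean is run "if the overall rate of study drug discontinuation due to lack of efficacy or AE is greater than 10" percent and the arms differ by more than 5 percentage points. Section 10.3 drops LOCF with the words "Thus, the PMM is sufficient to evaluate the robustness of the results from the MMRM".

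Section 8.1.1.1 sets the criterion: upper 95% limit at or below 1.5 mmHg at all nine timepoints and at or below 1.0 "mmHg at a majority (five or more) of the nine timepoints".

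**The concern.** Non-inferiority rests on a difference between arms, and a penalty applied equally to both largely cancels in that difference. What remains depends on whether one arm has more flagged values. The planned analysis therefore tests an imbalance in flagged missingness. It does not test whether the missing DE-117 values are worse than MAR predicts while timolol follows MAR, which is the departure that most directly threatens a non-inferiority claim.

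If the shares are similar, the conclusion may not tip anywhere between 1 and 5 mmHg, and step e would record that as robustness. Nothing else reliably covers the gap. The PPS analysis uses observed cases and so keeps the MAR assumption. The trimmed mean does not run when drug-discontinuation rates are similar, which is usually when the common delta says least. With LOCF removed, this is the only missing-data stress test that is always run.

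**Working it through.** **Inputs.** SAP section 3.3: 200 per arm, SD 4.0 mmHg, correlation 0.6, true difference 0, margin 1.5. Section 8.1.1.1: the 1.5/1.0 rule. Section 8.1.2: deltas of 1 to 5. The flagged shares pT (DE-117) and pC (timolol) are assumptions, because the documents give none.

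**The plan's own figure.** No figure is stated for the delta analysis. The nearest is 90% power. From the stated inputs, one timepoint at 1.5 gives 96.3%, all nine at 1.5 give 83.9%, and the full rule gives 72.5%. The 90% is therefore not reproduced under the nine-timepoint rule. That does not affect this point, but it explains why about 72% of simulated trials below succeed before any delta.

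**Formulas for one timepoint.** Delta is added after imputation, so:

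- shift = dT × pT − dC × pC. For a common delta d this is d × (pT − pC); for DE-117 only it is d × pT.
- upper limit = shift + 1.966 × √{[16 + dT² pT(1 − pT)]/200 + [16 + dC² pC(1 − pC)]/200}

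With no delta: 1.966 × √(32/200) = 1.966 × 0.400 = 0.79.

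Example, 10% flagged in each arm, delta 5, where 25 × 0.10 × 0.90 = 2.25:

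- Common: 0 + 1.966 × √(2 × 18.25/200) = 1.966 × 0.427 = 0.84.
- DE-117 only: 0.50 + 1.966 × √((18.25 + 16)/200) = 0.50 + 1.966 × 0.414 = 1.31.

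| Flagged DE-117 / timolol | Delta 5 applied to | Shift | Upper limit |
|---|---|---|---|
| 10% / 10% | both arms | 0.00 | 0.84 |
| 8% / 10% | both arms | −0.10 | 0.74 |
| 10% / 5% | both arms | +0.25 | 1.08 |
| 10% / 10% | DE-117 only | +0.50 | 1.31 |
| 5% / 5% | DE-117 only | +0.25 | 1.05 |

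Under a common delta of 5, the limit passes 1.0 once DE-117 has about 3 to 4 points more flagged values. Ignoring the added variance, the excess is (1.0 − 0.786)/5 = 4.3 points.

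**Check on the approximation.** A simulation with arm-specific multiple imputation (50 imputations), baseline adjustment and Rubin's rules gave these changes in the Month 3 upper limit at delta 5: +0.06 (common) against +0.53 (DE-117 only) at 10%/10%, and +0.04 against +0.27 at 5%/5%. The formula gives +0.05 against +0.53, and +0.03 against +0.26.

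**Full nine-timepoint rule.** The simulation used 6,000 trials with unadjusted means and monotone flags. The table shows the share of trials meeting non-inferiority at delta 0 that are then reversed.

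| Flags at Week 1 / Week 6 / Month 3 | Common delta 5 | DE-117-only delta 2 | DE-117-only delta 5 |
|---|---|---|---|
| 0/5/10% in both arms | 8.8% | 17.7% | 50.5% |
| 0/2.5/5% in both arms | 5.1% | – | 22.9% |
| 0/1/2% in both arms | about 3% | about 3% | about 8% |
| DE-117 0/5/10%, timolol 0/2.5/5% | 26.5% | – | – |
| DE-117 0/4/8%, timolol 0/5/10% | 3.1% | – | – |

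In the last row the overall pass rate rises from 71.8% to 73.2% under the common delta.

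**Month 3 mean diurnal IOP (limit 1.5).** SD = 4 × √((1 + 2 × 0.6)/3) = 3.43. With 10% flagged and a DE-117-only delta of 5, the limit is 0.50 + 1.966 × 0.359 = 1.21, so this test would hold.

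**The case against.** The algebra is not in dispute; the objections concern size and weight.

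- **A single timepoint above 1.0 is not a reversal.** This is correct. In the planning case with every estimated difference at 0 and flags of 0/2.5/5%, a DE-117-only delta of 5 gives limits of 0.79, 0.92 and 1.05 at the three visits. Six of nine timepoints stay at or below 1.0 and the rule holds. With flags of 0/5/10%, Month 3 passes 1.0 at delta 2.1, but the rule fails only at about 4.1, when Week 6 also crosses. The 1.5 limit is not reached until delta 6.7. The full-rule simulation is therefore the right measure of size.
- **Flagged shares may be low.** Subjects who stop drug are encouraged to stay to Visit 5, and early-exit assessments can map to Week 6 from Day 23 and to Month 3 from Day 62 (SAP sections 3.4 and 4.1.5). At 2% flagged by Month 3 the gap is only about 3% against 8%. This limits the consequence, but the plan gives no rate that would exclude the larger cases.
- **A common delta is a reasonable assumption.** The flagged reasons are the same in both arms, and a DE-117-only delta of 5 is a deliberate worst case. That supports keeping the common version. It does not make its result evidence of robustness when the shares are similar.
- **It is a supplementary analysis.** No primary estimate, decision rule or error rate changes. Section 7.1 already reports discontinuation by arm and reason, though not rescue censoring or flagged shares by visit.

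**Conclusion.** The concern holds. The common delta can challenge the non-inferiority conclusion when DE-117 has more flagged values. With similar shares it is nearly uninformative, and with more flagged timolol values it moves the result towards DE-117. In those two situations neither the robustness reading in step e nor the statement of sufficiency in section 10.3 is supported.

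The practical size depends on flagged shares that the documents do not give: large near 10% by Month 3, moderate near 5%, small near 2%. The nine-timepoint figures rest on the planning values, a true difference of 0 and unadjusted means, without imputation variance or baseline adjustment. The text supplied does not include the Appendix B code, so any arm-specific detail there could not be checked. The primary analysis stands; the recommendation is an inexpensive improvement that should be made.

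**What to change.** For the non-inferiority tests of the primary and key secondary endpoints, add to step b a delta of 1 to 5 mmHg applied to flagged DE-117 values only, with timolol left at MAR, or a two-way grid of arm-specific deltas. Keep the common-delta version beside it. Judge reversal of the nine-timepoint tests on the full rule, and of the Month 3 mean diurnal test on its 1.5 mmHg limit. Report the flagged share by arm and visit, so that the common-delta result can be interpreted, and amend the wording of step e and section 10.3 to match.

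The cost is SAP text and some added programming before unmasking, with no new data. The exact programming effort cannot be judged without the Appendix B code. The reported robustness may look less favourable.
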